#### **Systemic AESIs:**

Systemic AESI is defined as any acute systemic immediate allergic reactions (rapid onset) after exposure to a known or suspected allergen regardless of the causal relationship to the IMP, and occurring outside the DBPCFCs. This includes:

1. Anaphylactic reaction
2. Any systemic hypersensitivity reaction leading to epinephrine intake

Systemic AESIs will be identified by the investigator in the eCRF using the tick box “AESI”.

In case of serious events and to avoid duplicated information, SAE form is completed instead of AESI form. Serious systemic AESIs will be identified as any SAE with a preferred term (PT) corresponding to:

- “Anaphylactic reaction”
- “Anaphylactic shock”
- (“Hypersensitivity” or “Food allergy”) AND AE leading to an epinephrine intake (Epinephrine use will be retrieved using Standard medication name containing “EPINEPHRINE” and ATC level 1 = “CARDIOVASCULAR SYSTEM”)

#### 5.5.1.2 Handling of Missing or Incomplete Data

Partial AE end date will be derived before partial/missing AE start date.

CONFIDENTIEL / Ne pas diffuser sans autorisation de DBV

CONFIDENTIAL / Do not distribute without DBV authorization

	Statistical Analysis Plan	
	EPITOPÉ (V712-304) – Statistical Analysis Plan	
	Référence du Document /Document Reference : CCI	Page : 50 / 74

CCI

**AE end date**

- If AE end date is missing or AE is ongoing, the AE end date will not be imputed.
- If AE end date is partial:
  - If AE end day is missing, it will be imputed to the earliest date (last day of the month/Month AE end/Year AE end, death date)
  - If AE end day and month are missing, they will be imputed to the earliest date (31DEC/Year AE end, death date)

**AE start date**

- If AE start date is missing, the AE start date will not be imputed.
  - If derived AE end date is missing, the AE will be considered as TEAE
  - If derived AE end date is before (<) the Treatment start date, the AE will be considered as pre-TEAE
  - If derived AE end date is on or after (≥) the Treatment start date, the AE will be considered as TEAE
- If AE start date is partial:
  - If derived AE end date is missing:
    - If AE start day is missing it will be imputed to “01” unless month and year are the same as month and year of the TRT start date then impute TRT start date
    - If AE start day/month are missing they will be imputed to “01JAN” unless year is the same as year of the TRT start date then impute TRT start date
  - If derived AE end date is before (<) the Treatment start date:
    - Missing day will be imputed to 01 and Missing month will be imputed to “JAN”
  - If derived AE end date is on or after (≥) the Treatment start date:
    - If AE start day is missing it will be imputed to “01” unless month and year are the same as month and year of the TRT start date then impute TRT start date
    - If AE start day/month are missing they will be imputed to “01JAN” unless year is the same as year of the TRT start date then impute TRT start date

**Severity**

TEAEs with missing severity will be considered as “severe”;

**Causality**

TEAEs with missing relationship to the IMP will be considered as “drug-related”.

CONFIDENTIEL / Ne pas diffuser sans autorisation de DBV

CONFIDENTIAL / Do not distribute without DBV authorization

	Statistical Analysis Plan	
	EPITOPE (V712-304) – Statistical Analysis Plan	
	Référence du Document /Document Reference : CCI	Page : 51 / 74

CCI

TEAEs reported as related, probably related, or possibly related to the IMP will be considered as related to IMP.

### 5.5.1.3 Analyses

AEs related to accidental peanut consumption will be excluded from analyses (unless otherwise specified) and presented separately (section 5.7.1).

SAEs elicited during DBPCFC will be excluded from any analyses, unless otherwise specified. Nevertheless, these SAEs will be presented in the listings when applicable (section 5.6). Symptoms related to DBPCFC are reported in tables separately from other AEs.

For each summary presented by SOC and PT:

- the SOC “General disorders and administration site conditions” will be tabulated globally as well as split in 2 subsections:
  - General disorders (High Level Term not equal to “Application and instillation site reactions”),
  - Administration site conditions (High Level Term equal to “Application and instillation site reactions”).
- Lowest Level Term (LLT) will be tabulated for the PT “Anaphylactic reaction” to help distinguish reactions due to other allergens.

An overall overview table of TEAEs (to be distinguished from symptoms/reactions elicited during the DBPCFCs) will be provided showing the number of subjects, the percentage of subjects and the number of events for the following categories of TEAEs:

- Any TEAEs,
- Any serious TEAEs,
- Any TEAEs considered related to IMP:
  - Any TEAEs reported as related,
  - Any TEAEs reported as probably related,
  - Any TEAEs reported as possibly related,
- Any TEAEs considered unrelated to IMP:
  - Any TEAEs reported as unlikely related,
  - Any TEAEs reported as unrelated,
- Any Serious TEAEs considered related to IMP,
- Any TEAEs leading to permanent study treatment discontinuation,
- Any TEAEs leading to temporary study treatment discontinuation,
- Any TEAEs leading to death,
- Any mild TEAEs,

CONFIDENTIEL / Ne pas diffuser sans autorisation de DBV

CONFIDENTIAL / Do not distribute without DBV authorization

	Statistical Analysis Plan	
	EPITOPE (V712-304) – Statistical Analysis Plan	
	Référence du Document /Document Reference : CCI	Page : 52 / 74

CCI

- Any moderate TEAEs,
- Any severe TEAEs,
- Any severe TEAEs considered related to IMP (reported as related, probably or possibly related),
- Any IMP-induced Local TEAEs,
- Any severe IMP-induced Local TEAEs,
- Any treatment-emergent local AESI,
- Any treatment-emergent systemic AESI:
  - Reported as Anaphylactic reaction
  - Reported as Systemic hypersensitivity reaction leading to epinephrine intake
- Any treatment-emergent systemic AESI considered related to IMP (reported as related, probably or possibly related):
  - Reported as Anaphylactic reaction
  - Reported as Systemic hypersensitivity reaction leading to epinephrine intake
- Any TEAEs leading to an epinephrine intake
  - Considered related to IMP
  - Considered unrelated to IMP,
- Any TEAEs leading to systemic or inhaled corticosteroid use,
- Any TEAEs leading to topical corticosteroid use

Overall overview of TEAEs will be repeated:

- for the subgroups listed in section 5.2.5,
- including APC,
- for subperiod of treatment post 4 years old (from the date turning 4 years old to end of treatment).

The number and percentage of subjects who experienced at least one event and the number of events will further be summarized by SOC and PT for the following types of events:

- any TEAEs,
- any serious TEAEs,
- any potentially drug-related TEAEs,
- any serious potentially drug-related TEAEs,
- any TEAEs leading to permanent study treatment discontinuation,
- any TEAEs leading to temporary study treatment discontinuation,
- any TEAEs leading to death,
- any TEAEs leading to epinephrine intake,

CONFIDENTIEL / Ne pas diffuser sans autorisation de DBV

CONFIDENTIAL / Do not distribute without DBV authorization

	Statistical Analysis Plan	
	EPITOPÉ (V712-304) – Statistical Analysis Plan	
	Référence du Document /Document Reference : CCI	Page : 53 / 74

CCI

- any TEAEs leading to systemic or inhaled corticosteroid use,
- any TEAEs leading to topical corticosteroids use
- any TEAEs occurring after 407 days (V10 (365 + 7 days) + V11 (7 days) + V12 (4 weeks)).

Additional tables will be created to display the most frequent TEAEs (by preferred term), occurring in at least 5% of the subjects in any of the treatment groups.

For TEAEs and TEAEs considered related to IMP, additional tables will be provided showing number of subjects and percentage of subjects:

- By maximum severity (severe, moderate and mild): Subjects will be counted once per SOC and once per PT at the worst severity. If the severity is missing, the worst severity will be assumed.
- By maximum duration: For these tables TEAEs will be presented by SOC, PT within each SOC and maximum duration within each PT (using the classes for duration in days: (1 to 7 Days, 8 to 15 Days, 16 to 30 Days, 31 to 60 Days, 61 to 90 Days, More than 90 Days). For AEs ongoing at the end of the study, duration will be imputed based on the date of subject end of study. For AEs not ongoing but with missing end date, duration will be imputed based on date of last study treatment.

Additionally, for TEAEs and TEAEs considered related to IMP, tables showing number of subjects, percentage of subjects and number of events by severity will be provided. Subjects will be counted once per SOC, per PT and per severity. For these specific tables, if the severity is missing, no hypothesis will be assumed to replace the missing severity.

Adverse event summaries will be ordered in terms of decreasing frequency for SOC, and PT within SOC, in the active treatment group, and then similarly by decreasing frequency in the placebo group, and then alphabetically for SOC, and PT within SOC.

A by-subject listing of all adverse events will be provided. This listing will be presented by treatment group and will include: treatment group, subject identifier, age, sex, adverse event (SOC, PT, and verbatim term), date/time of onset (and corresponding study day), date/time of resolution (and corresponding study day), duration, severity, treatment required, relationship to IMP, relationship to an accidental peanut consumption, relationship to DBPCFC, and AESI flag, and action taken with the IMP, outcome, and whether the event is classified as serious or not with the corresponding criteria.

Pre-treatment emergent adverse events will be listed separately the same way as the treatment emergent adverse events.

TEAE leading to an epinephrine intake will also be listed.

Finally, SAEs will also be listed the same way with an additional flag for treatment emergent SAEs.

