### **6.4.4 Accidental Consumption of Peanuts**

Specific reactions triggered by accidental consumption of peanut and the conditions around that consumption will be collected with as much detailed information as possible, in particular with regard to the nature of the food and the quantity consumed. The subjects' parents/guardians will be asked to clarify whether any peanut consumption was accidental or not. The AEs induced by the consumption will be classified and analyzed separately.

As far as possible, a sample of the food having triggered the reactions will be collected and sent for analysis of its peanut content to a specialized laboratory. A specific procedure to organize the collection and the shipment of these samples will be provided to the centers and the subjects' parents/guardians.

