### 8.7 Exploratory Analyses

There will be no adjustments for multiplicity for any of the following exploratory analyses. The following exploratory analyses will be performed in the Safety Population:

- Analysis of IgE and IgG4 specific to peanut protein components: descriptive analysis will be conducted for IgE and IgG4 specific to peanut protein components using observed data;
- Analysis of total IgE, using the same statistical method as described for IgE and IgG4 specific to peanut protein components;
- Frequency of accidental peanut consumptions, conditions around the accidental consumptions (including the frequency of deliberate consumption to evaluate risk-taking behaviors), estimated quantity consumed at each occurrence, and associated reactions and severity of reactions will be studied on the Safety population;
- Descriptive analyses of epigenetic modifications of some specific genes in both treatment groups using observed data;
- Descriptive analysis will be conducted for each of the other allergen-specific IgE analyzed (cow's milk, egg, house dust mites, grass pollen) and the change from baseline will be tabulated using observed data;
- SCORAD change from baseline at Months 3, 6 and 12 will be presented using observed data;
- Quality of Life analysis using the EQ-5D-5L;
- Analyses of basophil activation: changes from baseline over time will be presented and correlation with DBPCFC outcomes will be explored;
- CCI [REDACTED]

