	EPITOPE (V712-304) – Statistical Analysis Plan	
	Référence du Document /Document Reference : CCI	Page : 32 / 74

CCI

- Any medication ATC code starting with “A07EA”, “C05”, “R01AD” and (ROUTE in “ORAL” “PO” “RECTAL” “RESPIRATORY (INHALATION)” “INTRAVENOUS”)
- Topical corticosteroids,
  - They will be identified as:
    - Any medication ATC code starting with “D07”
    - Any medication ATC code starting with “A07EA”, “C05”, “R01AD” and ROUTE = Topical.

For prior and/or concomitant medications, number and percent of subjects overall and per ATC class (level 3) and preferred drug name will be calculated. The following summaries will be presented overall and by treatment group for the Safety set:

- Prior medications (other than the ones taken during the food challenge at Baseline), prior only medications (P) will be taken into account;
- Concomitant medications (other than the ones taken for the food challenge at Month 12 and the ones taken for voluntary or accidental consumption of peanut), both prior and concomitant (PC) and concomitant (C) medications will be taken into account;
- Medications taken for food challenges, by time point;
- Concomitant medications taken due to accidental/voluntary consumption of peanut.

Number of antihistamine and number of epinephrine administrations during food challenges will also be tabulated separately (for the Peanut and Placebo days of DBPCFC separately), overall and by treatment group for the Safety set.

Non-drug therapies and surgical procedures are collected and will be coded using the version 20.1 of the MedDRA Dictionary. They will be also presented by SOC and preferred term overall and by treatment group for the Safety set.

All prior and concomitant medications, non-drug therapies and surgical procedures will be listed for the Safety set. The listing will be provided with a flag to indicate the prior and concomitant medications.

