### 5.5.1 Adverse Events

#### 5.5.1.1 Definitions

**Treatment-emergent AEs** will be defined as any AEs, regardless of relationship to IMP reported during or after the initial application, i.e. AEs where start date/time is on or after date/time of the first study treatment.

- When an AE's start date is equal to the date of first study treatment and the start time of AE is missing, AE will be defined as treatment emergent.
- Where dates are missing or partially missing, adverse events will be assumed to be treatment-emergent, unless there is a clear evidence (through comparison of partial dates) to suggest that the adverse event started prior to the first study treatment. More specifically, See Section 5.5.1.2.

AEs occurring after the end of the study will be recorded only if the investigator considers that there is a causal relationship with the IMP and as such, will be considered also as TEAEs.

**Pre-treatment emergent AE** will be defined as an AE that begins before the first administration of IMP.

**IMP-induced Local TEAEs** are defined as TEAEs considered as related to IMP with a High-Level Term equal to "Application and instillation site reactions" and will be flagged in the analysis datasets.

Following medication use will be defined:

- **Epinephrine use** will be identified by a combination of standard medication name that contains "EPINEPHRINE" and ATC level 1 = "CARDIOVASCULAR SYSTEM".
- **Systemic or inhaled corticosteroid use** will be identified by:
  - ATC code starting with "H02"
  - ATC code starting with "R03AK" (Adrenergics in combination with corticosteroids or other drugs, excl. anticholinergics) and "R03BA" (Glucocorticoids)
- **Topical corticosteroid use** will be identified by ATC code starting with "D07" (Corticosteroids, Dermatological preparations)

Treatment emergent adverse events of special interest (AESI), are defined as:

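### The SAP applies a narrower rule to adverse events than to medications: reactions to deliberately fed peanut are not separated, although their treatment is

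*SAP*

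**What the plan says.** **Protocol.** Section 6.4.4 provides that parents or guardians "will be asked to clarify whether any peanut consumption was accidental or not". Two sentences later in effect, it gives the analysis rule: "The AEs induced by the consumption will be classified and analyzed separately". Section 8.7 describes the exploratory analysis as covering the "conditions around the accidental consumptions (including the frequency of deliberate consumption to evaluate risk-taking behaviors", together with the quantity eaten, the associated reactions and their severity.

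**SAP, medications.** Section 5.3.7 leaves out of the concomitant-medication summary "the ones taken for voluntary or accidental consumption of peanut". It gives these medications a table of their own, accidental and voluntary together.

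**SAP, adverse events.** Section 5.5.1.3 states: "AEs related to accidental peanut consumption will be excluded from analyses (unless otherwise specified) and presented separately (section 5.7.1". In the same section, the AE listing carries an indicator for relationship to accidental consumption only, and the TEAE overview is to be repeated with APC included.

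**SAP, peanut consumption.** Section 5.7.1 counts subjects with any consumption, with consumption confirmed as accidental, and with consumption confirmed as non-accidental. Its AE overview and AE table are restricted to events induced by APC. The SAP abbreviation list does not define APC; in the protocol's list the letters stand for antigen-presenting cells.

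**The concern.** One event, a child reacting to peanut that was fed on purpose, meets two different rules. Its treatment is assigned to peanut consumption, but the reaction itself is not. The AE and medication outputs for peanut consumption then cannot be reconciled with each other.

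The all-causality safety rows would also hold some reactions to eaten peanut (the deliberate ones) but not others (the accidental ones). That matters most for infrequent categories that are central to the safety of a peanut patch, such as anaphylaxis, other systemic AESIs and TEAEs leading to epinephrine. A programmer working from the SAP could build the peanut-consumption AE table either way, because the term that sets its scope is undefined.

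**Working it through.** The plan states no figure on this point, so there is none to reproduce. The check follows one hypothetical event, a systemic reaction treated with epinephrine after deliberate feeding during treatment, through the SAP as written.

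1. **Is it a TEAE?** SAP 5.5.1.1 defines TEAEs as "any AEs, regardless of relationship to IMP reported during or after the initial application". Yes.
2. **Is it a systemic AESI?** The SAP definition covers acute systemic immediate allergic reactions "after exposure to a known or suspected allergen regardless of the causal relationship to the IMP, and occurring outside the DBPCFCs". Only food-challenge reactions are carved out. Yes, if it is anaphylaxis or led to epinephrine.
3. **Does the exclusion in 5.5.1.3 remove it?** That rule names accidental consumption only. No.
4. **Is it in the AE tables of 5.7.1?** They cover APC-induced events, while the same section counts accidental and non-accidental consumption separately. On the literal reading, no.
5. **Does the repeat overview including APC isolate it?** That overview adds accidental events back. It neither removes nor identifies deliberate ones. No.
6. **Where does its epinephrine go?** Under 5.3.7 it leaves the general concomitant-medication summary and enters the accidental/voluntary table. The row for TEAEs leading to epinephrine in 5.5.1.3 still counts the event.
7. **Does it enter the rows for events related to study product?** Only if the investigator judges it related or the causality is missing, since SAP 5.5.1.2 treats missing causality as drug-related.
8. **Is the narrower AE rule declared?** SAP 5.11 does not list it among the changes from the protocol.

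**Scale.** Inputs: the planned Part B arms of 233 active and 117 placebo subjects (protocol 3.1.2). For a child with no other event in the same category, the change in the arm's rate is 1/n:

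- active: 1/233 = 0.43 percentage points;
- placebo: 1/117 = 0.85 percentage points.

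The documents give no count of deliberate-feeding reactions. Assuming, purely for scale, 1 to 5 such children in one arm, the range is 0.43 to 5/233 = 2.1 points if they are in the active arm, or 0.85 to 5/117 = 4.3 points if they are in the placebo arm.

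**The case against.** The strongest reply is that APC serves as an umbrella label. SAP 5.7.1 says a dedicated form is completed for a possible APC, and consumptions are then counted as confirmed accidental or confirmed non-accidental, so the form seems to capture deliberate feeding too. Protocol 8.7 likewise places deliberate consumption inside its description of accidental consumption. If that is the intended meaning, AEs induced by APC would already include deliberate feeding. The reading is possible, but the SAP never states it. It also fits poorly with the accidental/non-accidental split in 5.7.1 and with 5.3.7, which names both types when it means both.

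A second reply is that the protocol does not clearly promise this analysis. Section 6.4.4 is headed as accidental consumption and opens with reactions to it. Section 3.3.3 ties reactions to accidental consumption and mentions voluntary consumption as risk-taking behaviour. That ambiguity stands: a reader might infer a plain breach of the protocol, and the text supports only a departure from its most natural reading. The mismatch inside the SAP remains either way.

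Third, keeping such events in all-causality rows agrees with the TEAE and AESI definitions and may be called cautious. This is fair, and it is why any fix must leave every event visible. It does not explain why accidental reactions are excluded and deliberate ones kept. Nor is retention reliably conservative, since these events could fall in either arm.

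A reader might also infer three stronger points that the documents do not support:

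- **Treatment use disappears.** It does not. The medications have their own table, and all medications are listed.
- **Patch-related rates are contaminated.** They change only under the conditions in step 7.
- **The comparison is biased because parents guess the arm from local reactions and test peanut more often on active treatment.** Protocol 3.4 reports local reactions in 90% to 98% for peanut doses of 50 to 250 µg but gives no placebo rate there. A strict peanut-free diet is required at entry and continues through the study. Nothing documents feeding that differs by arm.

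**Conclusion.** The point holds as a small inconsistency of scope. The SAP uses a wider rule for medications than for AEs arising from the same peanut consumption, and the narrower AE rule is neither defined nor declared. The consequence is confined to all-causality TEAE and systemic AESI rows and to agreement between the peanut-consumption AE and medication tables. The primary efficacy analysis is not involved.

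The conclusion rests on reading accidental and APC literally. If the sponsor meant APC to cover all consumption, what remains is a missing definition. The per-child increments above assume the planned arm sizes and no other qualifying event in that child; they indicate scale and are not an estimate of effect. With no count of deliberate feedings in the documents, the direction is as unknown as the size.

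**What to change.** Use one scope, any peanut consumption (accidental or voluntary), for AEs and medications:

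- In SAP 5.5.1.3, extend the separation rule to both types, matching 5.3.7.
- In SAP 5.7.1, give the AE overview and AE table for accidental, voluntary and either.
- In the AE listing, show the consumption type.
- Let the repeat TEAE overview that includes APC cover both types, so that no event is hidden.
- Define APC in the SAP. If the narrower AE rule was intended, say so and record it in 5.11 instead.

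The cost is a few sentences, some extra table rows and a link between the accidental/non-accidental field of the consumption form and the AE record. The link is needed because the listing indicator described now covers accidental consumption only. The main all-causality table would hold slightly fewer events, which the inclusive overview would show.

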No imputation will be performed for other efficacy, safety and exploratory parameters. In those instances, observed data will be used, excepted for laboratory results reported as below the lower detection limit (or reported above a specific value) which will be imputed as described in Section 5.1 and safety data where partial or missing data will be imputed according to the most conservative approach. (See section 5.5.1.2).

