## 5.2.6 Key dates, Relative days

### 5.2.6.1 Key dates

- **The date of first patch application** of each subject will be taken from the first exposure date from eCRF.
  - If only the day is missing, it will be imputed using the day of the latest date between the randomization date and the first dispensation date.
  - If day and month are missing, they will be imputed using the day/month of the latest date between the randomization date and the first dispensation date.
  - If the date is missing, it will be taken from first dispensation date.
- **The date of last patch application** of each subject will be taken from the last exposure date from eCRF.
  - If only the day is missing, it will be imputed to the last day of the month unless month and year are the same as month and year of study end date then impute study end date

CONFIDENTIEL / Ne pas diffuser sans autorisation de DBV

CONFIDENTIAL / Do not distribute without DBV authorization

	Statistical Analysis Plan	
	EPITOPE (V712-304) – Statistical Analysis Plan	
	Référence du Document /Document Reference : CCI	Page : 24 / 74

CCI

- If day and month are missing, they will be imputed to the 31st of December unless year is the same as year of study end date then impute study end date.
- If the date is missing because the subject was lost to follow-up, it will be derived from the study end date.
- **The study end date** will be derived as the study completion date or study discontinuation date from the disposition domain.
- If the date is missing, it will be derived as the last date available from the visits, the examination, the assessments.

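### The duration rule for resolved adverse events with no end date gives zero or negative values when onset is after the last patch

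*SAP*

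**What the plan says.** SAP 5.5.1.3 plans tables of TEAEs and of IMP-related TEAEs by maximum duration within each preferred term, using six classes: "1 to 7 Days, 8 to 15 Days, 16 to 30 Days, 31 to 60 Days, 61 to 90 Days, More than 90 Days". Two imputation rules feed them. The first covers ongoing events: "For AEs ongoing at the end of the study, duration will be imputed based on the date of subject end of study". The second covers events that have ended but lack an end date: "For AEs not ongoing but with missing end date, duration will be imputed based on date of last study treatment". The last-treatment date is defined in SAP 5.2.6.1; it "of each subject will be taken from the last exposure date from eCRF".

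SAP 5.5.1.1 defines TEAEs as "AEs where start date/time is on or after date/time of the first study treatment", with no cut-off at the last patch. It goes further: "AEs occurring after the end of the study will be recorded only if the investigator considers that there is a causal relationship with the IMP". Those events also count as TEAEs.

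On end dates, SAP 5.5.1.2 states: "If AE end date is missing or AE is ongoing, the AE end date will not be imputed". Partial end dates are completed there by separate rules, so the last-treatment rule bites only when the end date is entirely missing. SAP 5.2.4 gives the general principle, referring to "safety data where partial or missing data will be imputed according to the most conservative approach".

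**The concern.** Patch application ends at Visit 11 (Protocol 7.2.10). Children who do not enter the extension study return four weeks later (Protocol 7.2.11; SAP 3.1.3). SAP 5.5.1.3 also plans a separate table of TEAEs after Day 407, so it clearly expects events after treatment. For such an event the imputed end would precede the onset. The result is not a conservative value but an impossible one, and no class can hold it. The programmer would have to drop the event from the table or invent a rule after the plan is final. Duration is a TEAE summary planned in Protocol 8.6.1, so the rule should work for every event that the TEAE definition admits.

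**Working it through.** **The SAP's own timetable.** The Day 407 limit in 5.5.1.3 is built from Visit 10 (365 + 7), Visit 11 (7) and Visit 12 (four weeks): 365 + 7 + 7 + 28 = 407. It reproduces, and it confirms that TEAEs are counted after patches stop.

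**Assumptions.** The readable SAP text gives no formula for AE duration, and the appendices are redacted. I take duration = last patch day - onset day + 1, and also show the result without the + 1. Last patch on Day 372 and end of study on Day 400 are the target days for Visit 11 and end of study in SAP Table 2. The onset days are illustrative.

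**Onset after the last patch**
- One day after: (L) - (L + 1) + 1 = 0.
- 28 days after: (L) - (L + 28) + 1 = -27.
- Without the + 1: -1 to -28.

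The last patch day L cancels, so the range does not depend on it. Protocol 6.2.1.4 calls the follow-up two weeks rather than four; on that reading the range is 0 to -13. Every value is below the lowest class under either convention. Without the + 1, an event starting on the last patch day itself also gets 0 and has no class.

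**The two adjacent rules compared, onset Day 380**
- Ongoing at end of study: 400 - 380 + 1 = 21 days.
- Resolved, end date missing: 372 - 380 + 1 = -7 days.

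**Early discontinuation, assumed last patch Day 60, onset Day 70**
- 60 - 70 + 1 = -9 days.

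**Event spanning the last patch, onset Day 370, true end Day 395**
- True duration: 395 - 370 + 1 = 26 days (class 16 to 30).
- Imputed: 372 - 370 + 1 = 3 days (class 1 to 7).

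**Early onset, for contrast, onset Day 5**
- 372 - 5 + 1 = 368 days.
- Any onset up to Day 282 gives at least 372 - 282 + 1 = 91 days, hence the longest class.

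**The case against.** The best defence is that the case is rare. It needs late onset, resolution and a fully missing end date together. Protocol 6.2.1.4 requires a resolution date in every AE report, events are followed to resolution (Protocol 6.2.1.6), and queries are closed before unblinding (Protocol 5.4). Visit 12 is held only for children not entering the extension, and after early discontinuation the termination visit comes as soon as possible. This stands, and it limits the size of the problem; it does not supply the missing rule.

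Four stronger readings are tempting, and the documents do not support them.

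- **That early events are made falsely long.** The arithmetic above does put an early onset in the longest class. But the true duration is unknown, and running to the last patch is an upper bound if the event ended on treatment. That fits the stated conservative principle and its companions in SAP 5.5.1.2, where missing severity becomes severe and missing causality becomes drug-related. An unknown class for these events would be a preference, not a correction.
- **That 5.5.1.3 contradicts 5.5.1.2.** The latter governs end dates, which feed the treatment-emergent classification; the former imputes a duration for one set of tables. It does the same for ongoing events, whose end dates 5.5.1.2 also leaves alone. This is a tension, not a contradiction.
- **That itching, redness and swelling, entered as AEs in Part B, will make the problem common.** These symptoms are graded daily during treatment and the diary is collected at Visit 11, so they add little to post-treatment onsets. Their persistence is summarized separately, in days with a reaction (SAP 5.5.3), without AE end dates.
- **That one event sets the child's overall class.** The maximum is taken within a preferred term, so the effect stays in that row and its system organ class.

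**Conclusion.** The rule is wrong as written for a narrow set of events: resolved TEAEs with a fully missing end date and onset after the last study treatment. Over a four-week follow-up they get 0 to -27 days, or -1 to -28 without the assumed + 1; both ranges fall outside all six classes. Nothing else in the readable text corrects this. A lesser weakness is that the rule can understate an event that spans the last patch, as in the example of 3 days against 26, so it is only broadly conservative for on-treatment onsets.

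The effect is confined to the maximum-duration tables and any listed duration. Incidence, severity and efficacy are untouched. The documents do not say how many events are involved, and the number is probably small. This is a minor point, worth correcting because it costs so little.

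**What to change.** Add one sentence to SAP 5.5.1.3: a resolved TEAE with a fully missing end date and onset after the last study treatment is not imputed to the last treatment date. Then choose one of two treatments.

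- Show it in an added row for unknown duration.
- Impute to the subject's end-of-study date, as for ongoing events, never earlier than onset. That floor is needed because related events that start after the end of the study also count as TEAEs.

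The current rule may stay for on-treatment onsets, with imputed durations flagged in tables and listings so that an upper bound is not read as an observation. State the duration formula, including whether 1 is added, if the redacted appendices do not already do so.

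The cost is a sentence, a flag and at most one table row. Under the first option a few events carry no duration.
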